8.2.2 Efficacy Assessments

Efficacy will be determined by both clinical laboratory values and radiographic assessments (as outlined in Section [3](#)).

Radiographic Assessments

Radiographic assessments will be obtained as scheduled in [Table 1-3](#) irrespective of cycle duration including dose delays and treatment discontinuation. Standard radiological assessments should take place until clinically significant disease progression or deterioration, withdrawal of consent, or start of new anticancer therapy. Every assessment must include contrast-enhanced CT of the chest, abdomen, pelvis, and all other known sites of disease. The assessment should include MRI of the brain if a subject has signs or symptoms suggestive of CNS metastases. The assessment can be conducted earlier if clinical deterioration necessitates an earlier scan at the discretion of the managing physician. The same contrast and modality used at screening should be used for all subsequent assessments.

Tumor burden assessments will be performed based on RECIST 1.1 and iRECIST. RECIST 1.1 criteria will be used to determine eligibility based on the investigator's review of the radiographic data. Although tumor assessments following RECIST 1.1 will continue through the first disease progression (PD), iRECIST will be used and documented in eCRF to account for unique tumor response characteristics observed with immunotherapies and enable treatment decisions beyond progression (per RECIST 1.1). Tumor burden assessment performed at sites for decisions on treatment continuation will be based on iRECIST only and will continue until immune Confirmed Progression Disease (iCPD). Tumor burden assessments by the central core laboratory will be based on RECIST 1.1 and iRECIST. To confirm disease progression, a second CT scan must be performed 4-8 weeks after the first detection of radiographical progression. Responses (partial response [PR] and complete response [CR]) require confirmation by a repeat consecutive assessment at least 4 weeks after the first detection of radiographical response. Refer to the imaging manual for details on imaging assessments.

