For each subject at each timepoint, there is a separate RECIST 1.1 assessment and iRECIST assessment. Until PD has been reached, these assessments rely on the same measurements and NT/new lesion assessments. Subsequently, the assessments will differ as described above. Image acquisition for a subject should be kept consistent for the entire time the subject is on trial, including for the post RECIST 1.1 PD time points, which are assessed by iRECIST.

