4.2 Subgroups

Not applicable.

5. Definitions

Adverse events

An adverse event (**AE**) is any untoward medical occurrence in a clinical study subject irrespective of a causal relationship with the study treatment.

Age at enrollment

Subject age at enrollment will be determined using the age in years reported in the clinical database.

Area under the Curve (AUC)

The area under the **serum** drug concentration-time curve (AUC) reflects the actual body exposure to drug after administration of a dose of the drug.

Baseline

For any variable, unless otherwise specified, the baseline is the last non-missing assessment taken prior to the first administration of AMG 910.

For parameters/assessments not scheduled to be performed (or scheduled but not performed) on the same day as the first administration of AMG 910, the baseline value is the value from the screening period measured closest to the day of first administration of AMG 910.

Baseline ECG values in triplicate

The mean of values in a triplicate should be calculated for Baseline. Baseline triplicate value is the mean of all pre-dose assessments. For all post- baseline ECG, the mean value for measurements taken at the same assessment will be calculated and used in the analysis.

When an ECG is missing within a triplicate, all available data will be averaged for that time point.

Best Overall Response (BOR) - using RECIST v1.1 criteria

BOR is defined as the best response in the following order: CR, PR, SD, PD, or NE, where CR and PR require confirmation by a repeat consecutive assessment at least 4 weeks after the first detection of radiographical response or progressive disease. Confirmation of SD, minimum 6 weeks duration from the baseline scan is required. The details of derivation of BOR is described in [Appendix B](#).

Complete response (CR) per RECIST v1.1 criteria

Disappearance of all target lesions, non-target lesions and normalization of tumor markers. Any pathological lymph nodes (whether target or non-target) must have reduction in short axis to <10 mm.

Objective Response Rate (ORR) per RECIST v1.1 criteria

Objective response rate is defined as the proportion of patients with a BOR of CR or PR.

Partial Response (PR) per RECIST v1.1 criteria

Partial Response (PR) is defined as at least a 30% decrease in the sum of diameters of target lesions, taking as reference the baseline sum diameters. Non target lesions must be non-Progressive Disease (non-PD).

BMI

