14.2 Appendix B. RECIST (v1.1) Criteria

BOR will need to be derived based on timepoint response collected on RECIST 1.1 CRF.

Table 14-1 provides the BOR determination per RECIST 1.1 for trials where response confirmation is required. That means in the case of confirming CR or PR, a confirmation is required by a repeat assessment at least 4 weeks after the first detection and assessments of NE may occur between timepoint T1 and timepoint T2. For example, BL, CR, NE, NE, NE, CR – then CR at post baseline 1 is confirmed at post baseline 5. A BOR determined by **Table 14-1** is considered a **Confirmed_BOR**. At interim analysis, an unconfirmed response rate may be reported in addition to the confirmed response rate. The unconfirmed rate includes subjects who achieved a PR or CR and are awaiting a confirmative scan (i.e., unconfirmed responders). If these subjects have disease progression or death before the confirmative scan, then they are no longer considered as unconfirmed responder awaiting confirmative scan. Timepoint response “NON-CR/NON-PD” will be considered as “SD” in the algorithm of confirmation. **Interim_BOR** is defined to include these subjects in addition to **Confirmed_BOR**. **Table 14-2** outlines the steps to derive **Confirmed_BOR** and **Interim_BOR** given the timepoint assessments.

Table 14-1. BOR per RECIST 1.1

Criterion	Timepoint T1 Response	T1 ≥ 35* days after Baseline?	Timepoint T2 Response	T2 ≥ 35* days after Baseline?	T2 ≥ 28 days after T1?	BOR at time point T1
C1	CR	Yes	CR	-	Yes	CR
C2			CR	-	No	SD
C3			PR, SD	-	-	Query data**
C4			PD	-	-	SD
C5			NE, No further evaluations			SD
C6		No	CR	-	Yes	CR

C7		CR	Yes	No	SD	
C8		PR, SD	-	-	Query data**	
C9		PD	-	-	PD	
C10		NE, No further evaluations			NE	
C11	PR	Yes	CR, PR	-	Yes	PR
C12			CR, PR	-	No	SD
C13			SD	-	-	SD
C14			PD	-	-	SD
C15			NE, No further evaluations			SD
C16		No	CR, PR	-	Yes	PR
C17			CR, PR	Yes	No	SD
C18			SD	Yes	-	SD
C19			PD	-	-	PD
C20			NE, No further evaluations			NE
C21	SD	Yes	CR, PR, SD, PD, NE, no more evaluation		SD	
C22		No	CR, PR, SD	Yes	-	SD
C23			CR, PR, SD	No	-	NE
C24			PD	-	-	PD
C25			NE, No further evaluations			NE
C26	PD		-			PD
C27	NE	-	NE, No further evaluations			NE
C28		-	CR, PR, SD	Yes	-	SD
C29		-	CR, PR, SD	No	-	NE
C30		-	PD	-	-	PD

CR= complete response, PR= partial response, SD= stable disease, PD= progressive disease, and NE= not evaluable.

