*CR and PR need to be confirmed, which requires a repeat assessment at least 4 weeks after the first detection. Notice an unlimited number of intermittent assessments of NE can occur between the initial response and the confirmation. For example, CR, NE, NE, NE, CR – then CR at post baseline 1 is confirmed at post baseline 5. Both first detection and repeat assessment can be unscheduled visit and the 4 weeks apart rule needs to be met. For SD, a duration of at least 6 weeks after baseline scan is required. The threshold of 35 days accounts for the earliest available assessment by RECIST 1.1, as for tumor assessment per scheduling of imaging assessment.

**If a CR is truly met at timepoint T1, then any disease seen at a subsequent time point, even disease meeting PR criteria relative to baseline, makes progressive disease at that time point (i.e., disease must have re-appeared after CR). Best overall response would depend on whether minimum duration for SD was met. However, sometimes 'CR' may be claimed when subsequent scans suggest small lesions were likely still present and in fact the patient had PR, not CR at timepoint T1. Under this circumstances, the original CR should be changed to PR and the best response is PR.

Table 14-2. BOR Derivation Steps for GSP

Step 1. Derive Confirmed_BOR at each visit
Derive Confirmed_BOR at each visit:

 At Visit 1: Using the Visit 1 scan result and refer to Table 14-1 to derive Confirmed_BOR. At Visit 2 onward:

- (a) If current visit is CR or PR: Find last scan that is not NE or SD and at least 28 days before current visit. Derive *BOR_temp* as below:

Last scan	Current	BOR_temp
CR	CR	CR
PR	CR	PR
PR	PR	PR

- (b) If none of above fits, find last scan that is not NE, reference [Table 14-1](#) to derive *BOR_temp*.
- iii) Current visit *Confirmed_BOR* = best of (*BOR_temp*, last visit *confirmed_BOR*). Use rule CR > PR > SD > PD > NE

Step 2. Derive *Interim_BOR* at last visit prior to analysis data cutoff

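### The SAP's derivation of best overall response does not stop at first RECIST 1.1 progression, so any later visits held on the RECIST 1.1 CRF could turn PD into SD or a confirmed PR

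*SAP*

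**What the plan says.** SAP section 5 gives a ranking: "BOR is defined as the best response in the following order: CR, PR, SD, PD, or NE". It requires confirmation of CR and PR and a minimum duration for SD, but does not say that assessments after progression are left out.

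SAP Appendix B opens with the data source: "BOR will need to be derived based on timepoint response collected on RECIST 1.1 CRF". Table 14-2 Step 1 then works visit by visit:

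- Step ii(a), when the current visit is CR or PR: "Find last scan that is not NE or SD and at least 28 days before current visit". Three pairs have an outcome: CR then CR gives CR; PR then CR, or PR then PR, gives PR.
- Step ii(b): "If none of above fits, find last scan that is not NE", and read the result from Table 14-1.
- Step iii: keep the better of that result and the previous visit's value. "Use rule CR > PR > SD > PD > NE".

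Step 2, for the interim BOR, lists subjects with PD among those whose tumor assessment has ended, and copies their Step 1 value.

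On what is collected, protocol section 8.2.2 states: "Although tumor assessments following RECIST 1.1 will continue through the first disease progression (PD), iRECIST will be used and documented in eCRF". It also calls for a second CT 4 to 8 weeks after first radiographic progression, and site assessment under iRECIST continues until confirmed progression (iCPD). Protocol Appendix 12 states: "For each subject at each timepoint, there is a separate RECIST 1.1 assessment and iRECIST assessment". The same paragraph says that the two assessments differ after PD, and ends by describing timepoints after RECIST 1.1 PD as assessed by iRECIST.

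**The concern.** PD ranks below CR, PR and SD, and Step 1 runs at every visit with no stopping condition. A progression can therefore be overwritten by what is recorded later. In most trials this would be harmless, because scanning ends at progression. Here scans after RECIST 1.1 PD are part of the design, and treatment may continue on the strength of them.

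The result at stake is the only response rate that SAP section 9.5.2 tabulates: RECIST 1.1 objective response by planned dose level, shown with the counts in each BOR category. A response first seen after RECIST 1.1 progression is what iRECIST is there to capture, and the protocol lists objective response under both criteria. Counting such a response under RECIST 1.1 would raise that rate and blur the difference between the two. A move from PD to SD would leave the response rate alone but misstate the BOR table.

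**Working it through.** **Inputs.** Tables 14-1 and 14-2 of the SAP, applied as written. Scan days 42, 84, 140 and 196, from protocol Table 1-3 (every 6 weeks for 12 weeks, then every 8). All are past the 35-day threshold in Table 14-1, and consecutive scans are more than 28 days apart.

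**The plan's own figures.** The SAP example CR, NE, NE, NE, CR gives CR, as stated. The exact (Clopper-Pearson) 95% interval for 7/36 = 19.4% is 8.2% to 36.0%, matching the 8% to 36% in SAP section 3.2.

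**PD-PR-PR**
- Day 42: PD (row C26).
- Day 84: step ii(a) finds the PD at day 42, and PD then PR is not a listed pair. Step ii(b) takes that PD as T1, and row C26 gives PD. Step iii: best of (PD, PD) = PD.
- Day 140: step ii(a) finds the PR at day 84, 56 days earlier, and PR then PR gives PR. Step iii: best of (PR, PD) = **PR**.

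**PD-SD-SD**
- Days 42 and 84: PD, PD (row C26 both times).
- Day 140: T1 is the SD at day 84, and row C21 gives SD. Step iii: best of (SD, PD) = **SD**.

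**Further sequences**

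| Recorded responses | As written | Cut at first PD |
|---|---|---|
| PD-SD | PD | PD |
| PD-PR | PD | PD |
| PD-PD-PD | PD | PD |
| PD-SD-SD | SD | PD |
| PD-PR-PD | SD | PD |
| PD-PR-PR | PR | PD |
| SD-PD-PR-PR | PR | SD |
| PR-PD-PR-PR | PR | SD |

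**How many later visits are needed.** Two-scan sequences with PD first: 0 of 5 change, because row C26 holds the result at PD. Three-scan sequences with PD at scan 1 or 2: 5³ − 4×4×5 = 45. Two of these reach a data-query row, leaving 43. Of the 43, 13 change, and 3 of the 13 become responders (PD-PR-PR, PD-PR-CR, PD-CR-CR). All three need two evaluable scans after PD. Three of the other ten (PD-SD-NE, PD-PR-NE, PD-CR-NE) move to SD with one evaluable scan followed by a visit recorded as NE. These are counts of possible sequences, not patient frequencies.

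There is one off-schedule exception. With PR at day 42, PD at an unscheduled day 60 and PR at day 84, the PD is only 24 days before the last scan. Step ii(a) skips it, pairs the two PRs and returns PR; cut at first PD, the result is SD.

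**Size per subject wrongly counted as a responder**
- Dose level of 3: 1/3 = 33 points. Dose level of 4: 1/4 = 25 points.
- 36 subjects: 1/36 = 2.8 points. For example, 7/36 (19.4%; 8.2% to 36.0%) becomes 8/36 (22.2%; 10.1% to 39.2%).

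**The case against.** The strongest reply is that the algorithm would never see a visit after PD. Appendix B draws only on the RECIST 1.1 CRF, and protocol section 8.2.2 says that "tumor assessments following RECIST 1.1 will continue through the first disease progression (PD"). Appendix 12 ends by assigning later timepoints to iRECIST. Step 2 treats a subject with PD as finished with tumor assessment, and Appendix B drops an unconfirmed responder who progresses before the confirming scan. Read together, these suggest that the SAP's authors assumed no RECIST 1.1 entries after PD.

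Much of this stands. A reader might infer that nothing in the SAP limits the input, or that iRECIST responses flow into the RECIST 1.1 response rate. Neither is supported: the input is restricted to the RECIST 1.1 CRF, and iRECIST responses are not inputs. A reader might also infer that the ranking in step iii is enough by itself, or that the single CT required to confirm progression would overturn a PD. Row C26 prevents that on scheduled visits.

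What does not stand is that the path is closed. Appendix 12 also describes a RECIST 1.1 assessment at each timepoint and says that the two readings diverge after PD, which leaves RECIST 1.1 entries after PD possible. Step 2 gives no protection, since it passes on the Step 1 value unchanged.

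It is also fair that the sizes are simple denominator arithmetic, and that objective response is a secondary, descriptive endpoint with no test attached.

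**Conclusion.** The point holds as a conditional gap in the specification. Step 1 and the section 5 definition lack a cut-off at first RECIST 1.1 PD, and on inputs that the protocol leaves possible the stated steps return a better BOR than RECIST 1.1 assessment ending at first PD would give.

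Three conditions apply: visits after PD must be on the RECIST 1.1 CRF; they must be recorded there as SD, PR or CR rather than as continuing PD; and there must normally be at least two evaluable ones. The exceptions are those shown above: a second visit recorded as NE, which reaches only SD, and an off-schedule PD.

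The CRF is not among the documents, so the frequency is unknown and may be zero. The documents do not support saying that the reported response rate is inflated. If it happened, one subject would move the rate by 25 to 33 points in a dose level of 3 to 4. SAP section 7.1 says that the study was terminated early, so small denominators are the more relevant case; the 36-subject figure assumes a full expansion cohort.

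**What to change.** Add to the BOR definition in SAP section 5 and to Table 14-2 Step 1: RECIST 1.1 BOR uses only timepoints up to and including the first RECIST 1.1 PD. Reconcile protocol section 8.2.2 with Appendix 12, so that it is clear whether a RECIST 1.1 response is recorded after first PD.

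The cost is one sentence in two places, a date filter in the program, and a short clarification of the protocol. If no visits after PD are on the RECIST 1.1 CRF, no result changes.
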